10.2 Preparation and Administration of Atezolizumab

Preparation

Visually inspect drug product for particulate matter and discoloration prior to administration whenever solution and container permit. Atezolizumab is a colorless to slightly yellow solution. Discard the vial if the solution is cloudy, discolored, or visible particles are observed.

Do not shake the vial.

Prepare the solution for infusion as follows:

- Withdraw 20 mL of Atezolizumab from the vial.
- Dilute into a 250 mL polyvinyl chloride (PVC), polyethylene (PE), or polyolefin (PO) infusion bag containing 0.9% Sodium Chloride Injection, USP.
- Dilute with 0.9% Sodium Chloride Injection only.
- Mix diluted solution by gentle inversion. Do not shake.
- Discard partially used or empty vials of Atezolizumab.

10.2.1 Storage of Infusion

This product does not contain a preservative.

Administer immediately once prepared. If diluted Atezolizumab infusion solution is not used immediately, it can be stored either:

- At room temperature for no more than 6 hours from the time of preparation. This includes room temperature storage of the infusion in the infusion bag and time for administration for infusion.
- Under refrigeration at 2°C–8°C (36°F–46°F) for no more than 24 hours.

Do not freeze.

Do not shake.

10.2.2 Administration

Administer the initial infusion over 60 minutes through an intravenous line with or without a sterile, non-pyrogenic, low-protein binding in-line filter (pore size of 0.2–0.22 micron). If the first infusion is tolerated, all subsequent infusions may be delivered over 30 minutes. Do not co-administer other drugs through the same intravenous line.

10.3 Dose Modifications

No dose reductions of Atezolizumab are recommended.

Withhold/Permanently Discontinue Atezolizumab for any of the following:

Adverse Reaction	Severity*	Dose Modifications
Pneumonitis	Grade 2 pneumonitis	Withhold dose ^a
	Grade 3 or 4 pneumonitis	Permanently Discontinue
Hepatitis	Aspartate aminotransferase (AST)/or alanine aminotransferase (ALT) more than 3 and up to 5 times the upper limit of normal or total bilirubin more than 1.5 and up to 3 times the upper limit of normal	Withhold dose
	AST or ALT more than 5 times the upper limit of normal or total bilirubin more than 3 times the upper limit of normal	Permanently discontinue
Colitis or Diarrhea	Grade 2 or Grade 3	Withhold dose ^a
	Grade 4	Permanently discontinue
Symptomatic Hypophysitis, Adrenal Insufficiency, Hypothyroidism, Hyperthyroidism	Grade 2	Withhold dose ^a
	Grade 4 Hypophysitis	Permanently discontinue
Hyperglycemia	Grade 3 or Grade 4	Withhold dose ^a
Nephritis and Renal Dysfunction	Serum creatinine more than 1.5 and up to 6 times the upper limit of normal	Withhold dose ^a
	Serum creatinine more than 6 times the upper limit of normal	Permanently discontinue
Ocular inflammatory toxicity	Grade 2	Withhold dose ^a
	Grade 3 or 4	Permanently discontinue
Infection	Grade 3 and above	Withhold dose ^a
Pancreatitis	Grade 2 and above	Withhold dose ^a
Recurrent Pancreatitis	Grade 4 or any grade of recurrence	Permanently discontinue
Increase in amylase or lipase > 2.0 times ULN	Grade 3 and above	Withhold dose ^a
Infusion-related reactions	Grade 2 and above	Withhold dose ^a
	Grade 3 or 4	Permanently discontinue
Rash	Grade 3 rash	Withhold dose ^a
	Grade 4 rash	Permanently discontinue
Myasthenic syndrome/myasthenia gravis, Guillain-Barré or meningoencephalitis	All grades	Permanently discontinue

^a Resume treatment when adverse reaction returns to Grade 0 or 1.

* Toxicity was graded per National Cancer Institute Common Terminology Criteria for Adverse Events, Version 4.0 (NCI CTCAE v4).

11.0 Radiation Therapy Guidelines

11.1 Planning

After a lesion to be treated with radiotherapy is identified, the site is imaged at the time of CT simulation. Contrast Media may be used during the CT simulation, as deemed necessary by the treating physician. CT scan thickness should be <0.5 cm through the tumor bed region. These images will be used in treatment planning in accordance with the dose specific constraints per the Task Group 101 of the American Association of Physicists in Medicine.

The clinical tumor volume (CTV) is defined as the lesion of interest with the expected motion changes. The planning target volume (PTV) is the CTV + a 0.5-1 cm margin for setup error.

Respiratory gating may be used during the CT simulation to delineate an internal target volume (ITV) for chest and abdominal lesions that are subject to motion during the respiratory cycle. In this setting, a 0.5-1cm margin for setup error will be added to the ITV to establish the PTV.

Treatment Planning: 3D-Conformal or Intensity Modulated Radiation Therapy (IMRT) treatment planning is allowed. This includes “field-in-field” beams as well as the use of dynamic multi-leaf collimator (MLC) derived using inverse planning or electronic compensator techniques. Field arrangements and technique should be chosen that satisfy the PTV_{eval} and normal tissue dose constraints (TG101) using Dose-Volume Histogram (DVH) analysis by carefully selecting the gantry and table angle combinations that do not enter or exit through other organs of the body, the dose can be confined to the traditional treatment volumes. Non-coplanar beam arrangements are encouraged, but not required. Dose calculations with tissue inhomogeneity correction must be used. Beams entering lesions that will be monitored for abscopal responses will be avoided.

11.2 Treatment

Radiotherapy is delivered by external beam with a linear accelerator. The PTV is treated with radiation every other day (with a minimum of 36 hours between each fraction) starting on Day 1. A dose of 30 Gy in 3 fractions of 10 Gy each is delivered to an isodose surface encompassing the PTV.

The prescription dose is the dose delivered to a reference point within the CTV. The PTV receives a minimum of 90% of the prescription dose.

Treatment Machine: A linear accelerator with > 4 MV x-rays is required.

Immobilization Technique: Patients will be immobilized with a vac-loc or alpha cradle that is indexed to the treatment table.

Target Positioning Verification: Digitally acquired radiographic images will be used to verify the position of the target with respect to the treatment machine’s isocenter using digitally reconstructed radiographs (DRRs) or orthogonal (for IMRT) on the first day. Both kV and MV images may be used to verify setup.

Target Localization: Cone-beam CT (CBCT) images will be acquired prior to treatment for each fraction. By using image guided radiation treatment (IGRT) to image the tumor bed in “real-time”, the operator may automatically align the tumor bed with the treatment machine on each day of treatment.

11.3 Treatment modifications for Radiation Adverse Events

Dosing delay: except for radiation-associated mucositis and skin toxicity, the patient should have resolution or return to baseline of all grade 3-4 toxicities prior to the start of the next immunotherapy treatment.

12.0 Immunological Studies

12.1 Assessment of Baseline Immune Function

Baseline cellular/humoral immune function to tumor or defined antigens will be determined for each patient from peripheral blood obtained before the administration of investigational agents (radiation and PD-1/PDL-1). For patients with accessible tumor four punch biopsies measuring approximately 4-6mm of radiated and non-radiated tumor will be obtained to prepare tumor RNA.

12.2 On Study Evaluations

As summarized in the Study Calendar, patients are evaluated pre-treatment for definition of metastatic sites on with either CT scans or MRI. At least two measurable metastatic sites are identified. Non irradiated lesions will be followed and reported for responses per RECIST.

12.3 Off Study Criteria

- Intercurrent illness that prevents further administration of treatment
- Unacceptable toxicity
- Patient decides to withdraw from the study
- General or specific changes in the patient's condition render the patient unacceptable for further treatment in the judgment of the investigator

Authorized Physicians must notify the data manager and Principle Investigator when a patient is taken off study.

13.0 Prohibited and Restricted therapies during the Study

13.1 Prohibited Therapies

Patients in this study may not use vaccines for the treatment of cancer or prevention of disease unless indicated as a component of the protocol regimen (including those for common medical conditions) for up to one month pre and post dosing with nivolumab or atezolizumab. Concomitant systemic or local anti-cancer medications or treatments are prohibited in this study while receiving nivolumab/atezolizumab treatments.

Patients may not use any of the following therapies during the study:

- Any non-study anti-cancer agent (investigational or non-investigational);
- Any other investigational agents; Any other PD-1 or PDL-1 inhibitors;
- Immunosuppressive agents;
- Chronic systemic corticosteroids;

[figure not shown]
- Any non-oncology vaccine therapies used for the prevention of infectious diseases (for up to 30 days prior to or after any dose of study drug).

CONFIDENTIAL

14.0 Study Calendar

[figure not shown]
Arm A – Immunotherapy Alone

Renal Cell Carcinoma patients

Cohort 1

[figure not shown]
Urothelial Cancer patients

*Infusions will have a ± 3 day window to accommodate scheduling changes and holidays.

Arm B – Immunotherapy and Radiation

[figure not shown]
Renal Cell Carcinoma patients

Cohort 1

Arm B – Immunotherapy and Radiation

Urothelial Cancer patients

Cohort 2

*Infusions will have a ± 3 day window to accommodate scheduling changes and holidays.

15.0 Study Procedures and Observations - Nivolumab Alone and Nivolumab plus Radiation

Procedure	Screening Visit (- 28 days)	Day 1 ^h	Day 3 ^h	Day 5 ^h	Day 15 ^h	Day 29 ^h	Day 43 ^h	Day 57 ^h	Day 63 (+/-7 days)	F/UQ 9wks (±7days) for first year ^k	Follow up Q12 weeks (±7days) after 1 st year ^k years 2 and 3
Informed Consent	X										
Inclusion/Exclusion Criteria	X										
Medical History	X										
Pregnancy Test	X	X ^a				X ^a	X ^a	X ^a	X ^a		
Physical Examination Complete	X										
Physical Examination Limited		X				X	X	X	X	X	X
Vital Signs	X	X				X	X	X	X	X	X
Adverse Events Assessment	X	X				X	X	X	X	X	X
Serum Chemistry ^b	X	X				X	X	X	X	X	X
Hematology ^b	X	X				X	X	X	X	X	X
Urinalysis	X	X				X	X	X		X	X
CT (Chest, Abdomen, Pelvis) ⁱ	X								X	X ^d	Q 12 W
MRI Brain ⁱ	X										
Nivolumab infusion^j - ARM A		X			X	X	X	X			
Radiation Therapy^e - ARM B		X	X	X							
Endocrine Panels ^c	X				X	X	X	X			
Genomic Bloods/T-cell collection		X ^f				X ^f		X ^f			
Tumor biopsies	X ^g								X ^g		

a. Before each infusion.

b. SOC labs (COMP, CBC w/diff).

c. TSH, T3, T4

d. Scans day 63 ± 7.

e. Radiation is given to one, randomly selected lesion 30 Gy in 3 fractions of 10 Gy each (ARM B only)

f. to be collected PRIOR to infusion on days 1, 29 and 57.

g. Optional biopsy done at Day 63 (±7 days).

h. infusions will have a ± 3 day window.

i. prior scans will be valid until the screening period of 28 days

j. infusions will be ±24hrs from Day 1 of radiation. k. Patients will come off-study if they have disease progression. Patients will be followed for 30 days from the day they come off-study.

1.12 16.0 Study Procedures and Observations - Atezolizumab Alone and Atezolizumab plus Radiation

Procedure	Screening Visit (- 28 days)	Day 1 ^h	Day 3 ^h	Day 5 ^h	Day 22 ^h	Day 43 ^h	Day 64 ^h	Day 63 (+/-7days)	F/UQ 9wks (±7days) for first year ^k	Follow up Q12 weeks (±7days) after 1 st year ^k , years 2 and 3
Informed Consent	X									
Inclusion/Exclusion Criteria	X									
Medical History	X									
Pregnancy Test	X	X ^a			X ^a	X ^a	X ^a	X ^a		
Physical Examination Complete	X									
Physical Examination Limited		X			X	X	X	X	X	X
Vital Signs	X	X			X	X	X	X	X	X
Adverse Events Assessment	X	X			X	X	X	X	X	X
Serum Chemistry ^b	X	X			X	X	X	X	X	X
Hematology ^b	X	X			X	X	X	X	X	X
Urinalysis	X	X			X	X			X	X
CT imaging (Chest, Abdomen, Pelvis)	X							X	X ^d	Q 12 W
MRI Brain	X									
Atezolizumab/Pembrolizumab infusionⁱ - ARM A		X			X	X	X			
Radiation Therapy^e - ARM B		X	X	X						
Endocrine Panels ^c	X				X	X				
Genomic Bloods/T-cell collection		X ^f				X ^f	X ^f			
Tumor biopsies	X ^g							X ^g		

- a. Before each infusion.
- b. SOC labs (COMP, CBC w/diff.)
- c. TSH, T3, T4
- d. Scans day 63 ± 7.
- e. Radiation is given to one, randomly selected lesion 30Gy in 3 fractions of 10 Gy each (ARM B only)
- f. to be collected PRIOR to infusion on days 1,43 and 64.
- g. Optional biopsy done at Day 63(±7 days).
- h. infusions will have a ± 3 day window.
- i. prior scans will be valid until the screening period of 28 days,
- j. infusions will be ±24hrs from Day 1 of radiation. k. Patients will come off-study if they have disease progression. Patients will be followed for 30 days from the day they come off-study.

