9.0 Study Therapy [Nivolumab]

9.1 Nivolumab

Nivolumab is a human monoclonal antibody that blocks the interaction between PD-1 and its ligands, PD-L1 and PD-L2. Nivolumab is an IgG4 kappa immunoglobulin that has a calculated molecular mass of 146 kDa. Binding of the PD-1 ligands, PD-L1 and PD-L2, to the PD-1 receptor found on T cells, inhibits T-cell proliferation and cytokine production. Upregulation of PD-1 ligands occurs in some tumors and signaling through this pathway can contribute to inhibition of active T-cell immune surveillance of tumors. Nivolumab is a human immunoglobulin G4 (IgG4) monoclonal antibody that binds to the PD-1 receptor and blocks its interaction with PD-L1 and PD-L2, releasing PD-1 pathway-mediated inhibition of the immune response, including the anti-tumor immune response. In syngeneic mouse tumor models, blocking PD-1 activity resulted in decreased tumor growth.

Patients with Renal cell carcinoma will receive Nivolumab intravenously at a flat dose of 240mg every two weeks. Infusions will be given over 60 minutes (not bolus or IV push).

In Arm A:

Patient with Renal Cell carcinoma will receive nivolumab alone Days* 1, 15, 29, 43 and 57.

(* - infusions will have a \pm 3 days window to accommodate inevitable scheduling changes and holidays)

In Arm B:

Radiation is given to one lesion, 30 Gy in 3 fractions of 10 Gy each, over one week interval (with a minimum of 36 hours between each fraction), conformally or by intensity modulated radiation treatment to maximally spare normal tissue.

On the day of radiation (Day 1) immunotherapy is administered and repeated on the scheduled days. Patients will receive radiation on Day 1 and immunotherapy will be given \pm 24hr from Day 1.

Patients on both treatment arms will undergo re-imaging on Day 63 (\pm 7 days) (after the first 5 doses of Nivolumab) and every 9 (\pm 7 days) weeks for one year and every 12 weeks (\pm 7 days) thereafter. The first dose will be administered on Day 1 (\pm 24hrs) and repeated on Days 15, 22, 43 and 57. Radiation will be delivered every other day (with a minimum of 36 hours between the fractions) preferably starting on a Monday. A dose of 10 Gy x 3 days will be tested.

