9.3 Dose Modifications

Recommendations for nivolumab modifications are provided in Table 1. There are no recommended dose modifications for hypothyroidism or hyperthyroidism.

Interrupt or slow the rate of infusion in patients with mild or moderate infusion reactions. Discontinue nivolumab in patients with severe or life-threatening infusion reactions. Please refer to Table below for Recommended Dose Modifications.

Adverse Reaction	Severity*	Dose Modifications
Colitis	Grade 2 diarrhea or colitis	Withhold dose ^a
	Grade 3 diarrhea or colitis	Withhold dose ^a when administered as a single agent
	Grade 4 diarrhea or colitis	Permanently discontinue when administered with ipilimumab Permanently discontinue
Pneumonitis	Grade 2 pneumonitis	Withhold dose ^a
	Grade 3 or 4 pneumonitis	Permanently discontinue
Hepatitis	Aspartate aminotransferase (AST)/or alanine aminotransferase (ALT) more than 3 and up to 5 times the upper limit of normal or total bilirubin more than 1.5 and up to 3 times the upper limit of normal	Withhold dose
	AST or ALT more than 5 times the upper limit of normal or total bilirubin more than 3 times the upper limit of normal	Permanently discontinue
Hypophysitis	Grade 2 or 3 hypophysitis	Withhold dose ^a
	Grade 4 hypophysitis	Permanently discontinue
Adrenal Insufficiency	Grade 2 adrenal insufficiency	Withhold dose ^a
	Grade 3 or 4 adrenal insufficiency	Permanently discontinue
Type 1 Diabetes Mellitus	Grade 3 hyperglycemia	Withhold dose ^a
	Grade 4 hyperglycemia	Permanently discontinue
Nephritis and Renal Dysfunction	Serum creatinine more than 1.5 and up to 6 times the upper limit of normal	Withhold dose ^a
	Serum creatinine more than 6 times the upper limit of normal	Permanently discontinue

Rash	Grade 3 rash	Withhold dose ^a
	Grade 4 rash	Permanently discontinue
Encephalitis	New-onset moderate or severe neurologic signs or symptoms	Withhold dose ^a
	Immune-mediated encephalitis	Permanently discontinue
Other	Other Grade 3 adverse reaction First occurrence	Withhold dose ^a
	Recurrence of same Grade 3 adverse reactions	Permanently discontinue
	Life-threatening or Grade 4 adverse reaction	Permanently discontinue
	Requirement for 10 mg per day or greater prednisone or equivalent for more than 12 weeks	Permanently discontinue
	Persistent Grade 2 or 3 adverse reactions lasting 12 weeks or longer	Permanently discontinue

^a Resume treatment when adverse reaction returns to Grade 0 or 1.

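### The nivolumab calendar marks a Day 15 infusion without the pregnancy test its own footnote requires, and schedules no adverse-event, chemistry or haematology assessment there to support the hold rules

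*Combined protocol and SAP*

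**What the plan says.** Section 9.1 gives the Arm A dosing days: "Patient with Renal Cell carcinoma will receive nivolumab alone Days* 1, 15, 29, 43 and 57". Section 6.2 gives the same days for Arm B. In the Section 15.0 calendar the row "Nivolumab infusion^j - ARM A" is marked on those five days, Day 15 included. (The row label names Arm A only; the Arm B days come from Section 6.2.)

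The row "Pregnancy Test" is marked at screening and on Days 1, 29, 43, 57 and 63. From Day 1 on, its marks carry footnote a, which reads "Before each infusion". The rows "Adverse Events Assessment" and "Serum Chemistry ^b" are likewise marked on Days 1, 29, 43, 57 and 63 and blank on Day 15. The row "Endocrine Panels ^c" is marked on Day 15.

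Three sections make further dosing depend on toxicity:

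- Section 9.3 ties withholding or stopping nivolumab to adverse-event grades and to liver and creatinine thresholds. One criterion for permanent discontinuation is "AST or ALT more than 5 times the upper limit of normal or total bilirubin more than 3 times the upper limit of normal".
- Section 11.3 wants grade 3-4 toxicities, apart from radiation mucositis and skin toxicity, settled before the next immunotherapy dose.
- Section 27.2 holds treatment for haematological or non-haematological toxicity.

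**The concern.** A site that follows the calendar cell by cell would give the second nivolumab dose without a pregnancy test that the same table requires. It would also have no scheduled adverse-event assessment, chemistry or haematology on which to apply the hold rules.

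In Arm B this dose is the first after the radiotherapy fractions on Days 1, 3 and 5, so it is where the Section 11.3 rule first applies. Toxicity is a secondary objective, and the calendar sets when it is looked for systematically. The onset ranges quoted for nivolumab in renal cell carcinoma start at 2 days for pneumonitis, colitis and rash (Sections 3.6.1, 3.6.2, 3.6.6) and at 14 days for hepatitis (Section 3.6.3). Events by Day 15 are therefore possible, although the medians quoted there are 3 months or more.

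**Working it through.** No power or sample-size figure is involved. The check is a reading of the table and two subtractions.

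**1. Section 15.0, cell by cell.** Each row has 11 visit cells, and Day 15 is the fifth. The treatment-phase columns that matter are:

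| Row | Day 1 | Day 15 | Day 29 | Day 43 | Day 57 | Day 63 |
|---|---|---|---|---|---|---|
| Nivolumab infusion | X | X | X | X | X | – |
| Endocrine panel | – | X | X | X | X | – |
| Pregnancy test | X | – | X | X | X | X |
| Limited examination | X | – | X | X | X | X |
| Vital signs | X | – | X | X | X | X |
| Adverse events | X | – | X | X | X | X |
| Chemistry | X | – | X | X | X | X |
| Haematology | X | – | X | X | X | X |
| Urinalysis | X | – | X | X | X | – |

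Seven assessment rows are blank at Day 15 and one is marked.

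**2. Has a column shifted in the machine reading?** Two rows can be tested against other text. The research-blood row falls on Days 1, 29 and 57, as its footnote f says. The radiotherapy row falls on Days 1, 3 and 5, as the Schema says. The endocrine row is blank on Day 1 and marked on Day 15, so the Day 15 column is in use. A shift is unlikely but cannot be excluded without the source file. The Section 14.0 figures are not shown.

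**3. Comparison with Section 16.0.** All four infusions there (Days 1, 22, 43, 64) carry the pregnancy test, limited examination, vital signs, adverse-event assessment, chemistry and haematology. In Section 15.0, four of five infusions carry them. Across both calendars that is 4 + 4 = 8 of 9 marked infusions, and Day 15 is the exception. No reason is given.

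**4. What each rule requires at Day 15.**

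- Pregnancy test: footnote a requires it and the cell is blank. This is a direct contradiction. Section 8.1 asks for a test within 72 hours of starting study medication, which does not settle Day 15. The row also carries footnote a on Day 63, when no infusion is marked.
- Chemistry: Section 9.3 acts on AST/ALT, bilirubin and creatinine but sets no sampling frequency. Sections 3.6.3 and 3.6.5 ask for liver tests and creatinine before treatment and periodically during it.
- Haematology: the Section 9.3 table has no haematology threshold. The haematological hold is in Section 27.2, which gives no sampling days.
- Adverse-event grades: Sections 9.3, 11.3 and 27.2 all use them, and none is scheduled to be assessed at Day 15.

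**5. Intervals between scheduled adverse-event assessments.**

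- Section 15.0: Day 29 − Day 1 = 28 days.
- Section 16.0: Day 22 − Day 1 = 21 days.
- Arm B on nivolumab, from the last fraction on Day 5: 29 − 5 = 24 days to the next scheduled assessment. The second infusion falls 15 − 5 = 10 days after that fraction.

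**6. Who is affected.** Section 29.0 assumes about 20 patients a year in each cohort out of 40. That is 20/40 = one half, or about 56 of 112 in the renal cohort. The Schema and Sections 6.2 and 10.1 also allow nivolumab for urothelial patients; their number is not stated.

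**7. A related conflict.** Later in Section 9.1 the repeat doses are listed as Days 15, 22, 43 and 57, against Days 15, 29, 43 and 57 earlier in the same section. Day 15 is on both lists.

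**The case against.** The best defence is that most of the blank column breaks no stated rule. Footnote a belongs to the pregnancy-test row alone. Chemistry and haematology carry footnote b, and the adverse-event row carries none. Draws on Days 1 and 29 can be read as periodic monitoring. The calendars do not tie an assessment to every dose throughout the trial either: treatment may run for three years, yet neither calendar marks infusions after Day 57 or Day 64, and adverse-event assessments then fall every 9 or 12 weeks. All of this stands. It limits the literal contradiction to the pregnancy test, which in practice concerns women of childbearing potential, and it limits the count in step 3 to marked infusions.

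A reader might infer more: that the second dose is unmonitored, that the hold rules cannot be applied to it, or that early toxicity of the combination is recorded late. The documents do not support this. The endocrine panel is taken that day. Many Section 9.3 items are clinical and can be recognised without a laboratory draw, and Sections 11.3 and 27.2 apply whatever the grid shows. Section 21.1 covers events reported by patients or observed by staff, Section 21.4 logs all of them, Section 21.7 requires serious events to be reported within 24 hours, and Section 27.1 has a monthly review. What is missing is a scheduled check. Nor does a biased arm comparison follow, since the nivolumab calendar is the same in both arms.

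The defence does not explain why Day 15 alone among the marked infusions lacks these checks, and it does not remove the conflict between footnote a and its own row.

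**Conclusion.** The point holds in two parts of different strength. The pregnancy-test row is wrong as written, because it omits a test that its footnote requires. The other six blank rows are an operational gap: three hold rules depend on toxicity status, and the calendar schedules no adverse-event, chemistry or haematology assessment at the second dose.

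The size is one of five marked nivolumab infusions and a 28-day interval to the next scheduled adverse-event assessment, 7 days longer than in Section 16.0. It affects every patient on nivolumab: about 56 if the cohorts accrue equally, which is a planning rate and not a fixed allocation, plus any urothelial patients given nivolumab. The pattern suggests an oversight, but the documents do not say so.

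The conclusion assumes that the table was read correctly; confidence is medium until the source is checked. It should be corrected, but it does not affect the primary analysis.

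**What to change.** Check the source table and the Section 14.0 figures first. If the Day 15 column is as read here, reconcile it with footnote a, with the hold rules in Sections 9.3, 11.3 and 27.2, and with the two dosing lists in Section 9.1. If any blank is intended, say so and state how the hold rules are to be applied at that dose. The sponsor decides what the column should contain; no monitoring or dosing rule is proposed here.

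If patients have already passed Day 15, establish what was collected at that visit and report it with the toxicity results.

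The cost is a calendar correction and, depending on the sponsor's decision, a small amount of added work at a visit that already takes place.
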